8.10 IMMUNOGENICITY ANALYSES

Post-baseline cellular and humoral response magnitude may be compared between treatment groups using a difference in medians and associated non-parametric 95% CI. Post-baseline tissue response magnitude will be compared between treatment groups using a difference in means and associated t-distribution based 95% CIs.

Valid samples for statistical analysis purposes will be those collected within 7 or 14 days of the specified time points (see Table 1). Baseline is defined as the last measurement prior to the first treatment administration.

8.11 SAFETY ANALYSES

8.11.1 ADVERSE EVENTS

All AEs will be summarized among the safety population by frequency per treatment arm. These frequencies will be presented overall and separately by dose, and will depict overall, by system organ class and by preferred term, the percentage of subjects affected. Additional frequencies will be presented with respect to maximum severity and to strongest relationship to Study Treatment. Multiple occurrences of the same AE will be counted only once following a worst-case approach

with respect to severity and relationship to Study Treatment. All serious AEs will also be summarized as above.

The main summary of safety data will be based on events occurring within 14 days of any dose. For this summary, the frequency of preferred term events will be compared between study arms with risk differences and 95% confidence intervals, using the method of Miettinen and Nurminen [27]. As this analysis will use many event categories, and produce many confidence intervals, caution should be exercised when interpreting these confidence intervals. Separate summaries will be based on events occurring within 7 days of any dose and regardless of when they occurred.

Any AEs with a missing or partial onset date will be included in the overall AEs, but not be included within specified day-range summaries. AE duration will be calculated as (Stop Date – Start Date) + 1.

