3.3 SECONDARY OBJECTIVES AND ASSOCIATED ENDPOINTS

Secondary Objectives	Associated Endpoints	
 Evaluate the safety and tolerability of VGX- 3100X delivered IM followed by EP with CELLECTRA™ 5PSP 	 1a. Incidence and severity of local and systemic events for 7 and 28 days following each investigational treatment and for the duration of the study (through Week 88 visit) 1b. Incidence and severity of serious adverse events (SAE) and Unanticipated [Serious] Adverse Device Effects (UADE) for 7 and 28 days following each investigational treatment and for the duration of the study (through Week 88 visit) 	
2. Determine the efficacy of VGX-3100X compared with placebo as measured by histopathologic regression of cervical HSIL	2. Proportion of subjects with no evidence of cervical HSIL on histology (i.e. biopsies or excisional treatment) at Week 36 visit	
3. Determine the efficacy of VGX-3100X compared with placebo as measured by virologic clearance of HPV-16 and/or HPV-18	3. Proportion of subjects with no evidence of HPV-16 and/or HPV-18 in ThinPrep [™] cervical samples by type specific HPV testing at Week 36 visit	

Secondary Objectives	Associated Endpoints		
4. Determine the efficacy of VGX-3100X compared with placebo as measured by complete histopathologic regression of cervical HSIL to normal	4. Proportion of subjects with no evidence of LSIL or HSIL (i.e. no evidence of CIN1, CIN2 or CIN3) on histology (i.e. biopsies or excisional treatment) at Week 36 visit		
5. Determine the efficacy of VGX-3100X compared with placebo as measured by both complete histopathologic regression of cervical HSIL to normal and virologic clearance of HPV-16 and/or HPV-18	5. Proportion of subjects with no evidence of LSIL or HSIL (i.e. no evidence of CIN1, CIN2 or CIN3 on biopsies or excisional treatment) on histology (i.e. biopsies or excisional treatment) and no evidence of HPV-16 and/or HPV-18 by type specific HPV testing at Week 36 visit		
6. Determine the efficacy of VGX-3100X compared with placebo as measured by histopathologic non-progression	6. Proportion of subjects with no progression of cervical HSIL from baseline on histology (i.e. biopsies or excisional treatment) at Week 36 visit		

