2.3 SAFETY MONITORING PLAN

Although cervical HSIL is thought to require years to progress to cervical cancer, subjects in the Phase 2b study were followed closely throughout. HPV testing (Weeks 14 and 24), cytology (Week 14) and colposcopy (Week 24) were all mandatory during the observation period prior to obtaining tissue for determination of the primary histologic endpoint at Week 36. Investigators were also instructed to perform additional testing (including biopsy) if disease progression was suspected. These instances were infrequent as only 11 unscheduled biopsies were deemed necessary over the course of the Phase 2b study. In addition, the rate at which occult microinvasive cancer was discovered after 36 weeks was less frequent than what is reported in the literature [22]. Both observations would imply that the mandatory monitoring employed in the Phase 2b study was sufficient; however cervical disease will be monitored even more closely in this Phase 3 study. Colposcopy, cytology and HPV testing will be required at 8 to 14 week intervals throughout the observation period leading up to the primary endpoint 36 weeks after the first dose. Although less frequent monitoring may be adequate, the more frequent monitoring is designed to afford an even wider margin of safety and an opportunity to explore predictors of efficacy.

Safety monitoring will include:

- Local and systemic events for 7 days following each treatment as noted on a Participant Diary Card (PDC).
- All adverse events including SAEs, UADEs, and other unexpected AEs for the duration of the study;

In the Phase 2b study, the safety profile was carefully evaluated and treatment with VGX-3100 was well-tolerated based on observations through Week 88 in all subjects. The most common adverse events were administration-site reactions, which included pain, tenderness, erythema and swelling, and were generally mild and limited to a few days in duration. Only erythema showed a statistically higher incidence in VGX-3100 (78%) vs. placebo (57%) in the 7- and 28-day periods after a dose. One additional AE, sinusitis, was also statistically significantly increased over the course of the entire study period but resolved without sequelae in the VGX-3100 arm compared to the Placebo arm (10% vs. 0%).

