3.3 SECONDARY OBJECTIVES AND ASSOCIATED ENDPOINTS

Secondary Objectives	Associated Secondary Endpoints
	1a. Incidence and severity of local and systemic
VGX-3100 delivered IM followed by EP	events for 7 and 28 days following each
with CELLECTRA [™] 5PSP	investigational treatment and for the duration
	of the study (through Week 88 visit)
	1b. Incidence and severity of SAE and UADE for 7
	and 28 days following each investigational
	treatment and for the duration of the study
	(through Week 88 visit)
2.Determine VGX-3100 efficacy compared	2
to placebo as measured by histopathologic	cervical HSIL on histology (i.e. biopsies or
regression of cervical HSIL	excisional treatment) at Week 36 visit
3.Determine VGX-3100 efficacy compared	3. Proportion of subjects with no evidence of HPV-
to placebo as measured by virologic	16 and/or HPV-18 in cervical samples by type
clearance of HPV-16 and/or HPV-18	specific HPV testing at Week 36 visit
4.Determine VGX-3100 efficacy compared	
to placebo as measured by complete	grade squamous intraepithelial lesion (LSIL) or
histopathologic regression of cervical	,
HSIL to normal	on histology (i.e. biopsies or excisional
	treatment) at Week 36 visit
5.Determine VGX-3100 efficacy compared	1
to placebo as measured by both complete	or HSIL (i.e. no evidence of CIN1, CIN2 or
histopathologic regression of cervical	CIN3 on biopsies or excisional treatment) on
HSIL to normal and virologic clearance of	histology (i.e. biopsies or excisional treatment)
HPV-16 and/or HPV-18	and no evidence of HPV-16 and/or HPV-18 by
	type specific HPV testing at Week 36 visit
6.Determine the efficacy of VGX-3100	
compared with placebo as measured by	cervical HSIL to cervical carcinoma from
histopathologic non-progression	baseline on histology (i.e. biopsies or excisional
	treatment) at Week 36 visit
7.Describe the clearance of HPV-16 and/or	
HPV-18 infection from non-cervical	and/or HPV-18 on specimens from non-cervical
anatomic locations	anatomic locations (i oropharynx, vagina and
	intra-anal) at Week 36 Visit
	8a. Levels of serum anti-HPV-16 and anti-HPV-18
immune response following administration	antibody concentrations at baseline, Week 15,
of VGX-3100 compared with placebo at	36, and 88 visits
	8b. Interferon-γ ELISpot response magnitudes at
compared to baseline	baseline, Weeks 15, 36, and 88 visits
	8c. Flow Cytometry response magnitudes at
	baseline and Week 15 visits

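### The 28-day safety endpoint has no matching analysis: the only between-arm comparison with confidence intervals uses a 14-day window that no endpoint names

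*Protocol*

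**What the plan says.** Section 3.3 of the Protocol defines secondary endpoint 1a as "Incidence and severity of local and systemic events for 7 and 28 days following each investigational treatment and for the duration of the study", through the Week 88 visit. Endpoint 1b uses the same three windows for serious adverse events and unanticipated adverse device effects. Version 3.0 keeps these windows in both its synopsis and its Section 3.3: "events for 7 and 28 days following each" treatment, plus the whole study.

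The analysis is set out in Section 8.11.1. The latest text shown is that of the version before 3.0, which the change list numbers 2.1. It contains four relevant statements:

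- A general tabulation: "All AEs will be summarized among the safety population by frequency per treatment arm", given overall and by dose, by system organ class and preferred term.
- The main summary: "The main summary of safety data will be based on events occurring within 14 days of any dose".
- The comparison attached to it: "For this summary, the frequency of preferred term events will be compared between study arms with risk differences and 95% confidence intervals", by the Miettinen-Nurminen method.
- The remaining summaries: "Separate summaries will be based on events occurring within 7 days of any dose and regardless of when they occurred".

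Section 2.3 reports that in Phase 2b erythema was more frequent on VGX-3100 than on placebo (78% vs 57%) "in the 7- and 28-day periods after a dose".

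**The concern.** The endpoint section and the analysis section name different windows. Section 3.3 asks for 28 days and Section 8.11.1 never does. Section 8.11.1 makes 14 days the main window and no objective asks for that.

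This is more than detail left to a statistical analysis plan, because the Protocol itself fixes the 14-day window as the main one. A plan that follows Section 8.11.1 leaves the 28-day endpoint without a matching table. A plan that follows Section 3.3 departs from Section 8.11.1.

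At stake is the between-arm reading of events in the third and fourth weeks after a dose. The study collects data there: adverse events are recorded throughout, and Section 6.6 schedules injection-site assessment two to four weeks after treatment. Phase 2b results were reported for 28 days, and this trial would have no planned counterpart to set beside them.

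**Working it through.** There is no sample size, power or alpha figure to reproduce for this point. The check compares the two sections and then counts calendar days.

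**Windows side by side**

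| Window | Endpoint (3.3) | Summary planned (8.11.1) | Risk difference and 95% CI specified (8.11.1) |
|---|---|---|---|
| 7 days | yes | yes | no |
| 14 days | no | yes, the main one | yes |
| 28 days | yes | **no** | **no** |
| Whole study | yes | yes | no |

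The only window with a specified interval is the one that is not an endpoint. The only endpoint window without a summary is 28 days.

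**Days left out of the 14-day comparison**

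Inputs: doses on Day 0, Week 4 (Day 28) and Week 12 (Day 84), with Weeks 4 and 12 each allowed ±4 days (synopsis and Schedule of Events). The day of dosing counts as inside the window, and a calendar day that falls in two windows is counted once.

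Nominal schedule:

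- 28-day windows: Days 0–28, 28–56 and 84–112. The first two join into Days 0–56, which is 57 days; the third is 29 days. 57 + 29 = 86.
- 14-day windows: Days 0–14, 28–42 and 84–98. 15 + 15 + 15 = 45.
- Inside 28 days of a dose but not within 14 days of any dose: Days 15–27 (13), 43–56 (14) and 99–112 (14). 13 + 14 + 14 = 41.
- Share left out: 41 / 86 = 0.477, about 48%.

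Dose 2 early, on Day 24:

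- 28-day windows: Days 0–52 (53 days) plus 29 days = 82.
- Left out: Days 15–23 (9), then 14 after dose 2 and 14 after dose 3. 9 + 14 + 14 = 37.
- Share: 37 / 82 = 0.451, about 45%.

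Dose 2 late, on Day 32:

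- 28-day windows: three separate windows of 29 days = 87.
- Left out: 14 + 14 + 14 = 42.
- Share: 42 / 87 = 0.483, about 48%.

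Moving dose 3 within its ±4 days changes none of these totals. The range is therefore 37 to 42 days, or 45% to 48%.

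**With a 28-day comparison added**

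The days covered by a specified comparison rise from 45 to 86 on the nominal schedule. An event count cannot be derived, because the documents give no event rate for days 15–28.

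**The case against.** The strongest reply is that little is lost. Section 8.11.1 tabulates all adverse events by arm, overall and by dose, with severity and relationship, and adds a summary regardless of timing. Two of the three endpoint windows are covered. The common reactions in Phase 2b were generally mild and lasted a few days, and a 14-day window fits the scheduled contact 8 to 14 days after each dose.

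Most of this stands, and it rules out some stronger readings that a reader might infer:

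- *That days 15–28 are never compared, or that the safety endpoint goes unanalysed.* Events on those days are tabulated by arm. What is missing is a 28-day window and an interval for it.
- *That nothing can be set beside Phase 2b.* The 7-day result can; only the 28-day result lacks a counterpart.
- *That exactly half the risk time is lost*, from 3 × 28 = 84 days against 3 × 14 = 42. That product ignores the dosing days and the overlap of windows. The calendar count gives 45% to 48%, and days are not events.
- *That the rule for onset dates is a second error.* Section 8.11.1 says: "Any AEs with a missing or partial onset date will be included in the overall AEs, but not be included within specified day-range summaries". Those events stay in the overall tables. The more inclusive rule in Section 8.8 belongs to the split between prior and concomitant medication, a different purpose. This is a choice of convention, and the documents show no effect of it.

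The version is a fair limit too. The Section 8.11 text of version 3.0 is not shown. Its change list describes Section 8 changes on missing data and a subgroup analysis, names no change to the adverse event window, and calls unlisted changes administrative. That makes it likely, but not certain, that the 14-day wording persists.

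None of this supplies the missing 28-day summary. A count over 88 weeks does not show what happened within 28 days of a dose.

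**Conclusion.** The mismatch is real and certain within the version before 3.0, where both sections can be read. The 28-day part of endpoints 1a and 1b has no planned analysis, and the main comparison uses a window that matches no endpoint. On the nominal schedule, 41 of 86 days (48%) fall outside that comparison, and 45% to 48% across the permitted timing of dose 2.

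These figures assume that all three doses are given, that the day of dosing is counted, and that the 14-day window applies after any dose, as written. They measure time covered, not events missed. The documents do not show that a safety conclusion would change. For version 3.0 the endpoint windows are confirmed and the analysis window is not.

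**What to change.** In Section 8.11.1, add a summary of events occurring within 28 days of each dose, with the same Miettinen-Nurminen risk differences and 95% confidence intervals now specified for the 14-day summary. Apply it to serious adverse events and device effects as well, since endpoint 1b uses the same window. Keep the 7-day and overall summaries. The 14-day table may stay as an additional one.

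Then confirm that Section 8.11.1 of version 3.0 carries the same wording.

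The cost is a sentence or two of text and one more set of tables and intervals. Section 8.11.1 already cautions that the number of intervals calls for care in interpretation, and this adds to that number. No new data collection is needed.

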8.11.2 LABORATORY DATA

Continuous response variables per time point and changes from baseline will be summarized with mean, median, minimum, and maximum values, and categorical response variables will be summarized per time point with percentages, by treatment arm. Baseline is defined as the last measurement prior to the first treatment administration.

8.12 VITAL SIGNS

Measurements for vital signs as well as changes from baseline will be summarized with descriptive statistics: mean standard deviation, minimum, median, and maximum values by time point and treatment arm, for the mITT population. Baseline is defined as the last measurement prior to the first treatment administration.

8.13 PHYSICAL EXAMINATION

The percentage of subjects with abnormal physical examination findings at each time point will be summarized by treatment arm and by body system, for the mITT population.

8.14 PATIENT REPORTED OUTCOMES

As an exploratory endpoint, patient reported outcomes among subjects who receive VGX-3100X will be compared between those with excision versus those without excision, based on PRO endpoints. This comparison will utilize the median difference in endpoints or the difference in proportions of subjects with endpoints and associated non-parametric or Miettinen and Nurminen [27] 95% CIs, for continuous responses and binary responses, respectively.

8.15 MISSING VALUES

Missing data will not be imputed or replaced, and calculations will be done on reported values.

A subject's regression outcome is missing if her CIN grade and HPV clearance at Week 36 cannot be determined. Any subject who had suspected disease progression before Week 36 will be considered a non-regressor regardless of the Week 36 result, even if missing.

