2.1.3 DEFINITION OF RESPONDER AND NON-RESPONDER

Responder and non-responder definitions (Table 7) for the primary endpoint takes into account both histopathologic regression of cervical HSIL and virologic (HPV-16 and/or HPV-18) clearance from cervical samples since HPV persistence is an important factor in the clinical progression of HSIL. The responder definition also excludes subjects whose cervix is biopsied at any time between their initial biopsy to determine eligibility and the Week 36 endpoint tissue collection. This exclusion is included to reduce the potential for artefactual increases in the treatment effect caused by removal of HSIL tissue and potentially HPV-16/-18 by unplanned interval biopsies. To qualify as a responder, the subject must have: 1) an acceptable histology specimen at Week 36, which is interpretable by the independent PAC, and 2) an acceptable HPV ThinPrepTM sample at Week 36, with an associated valid HPV-testing result. A responder is defined as a subject with: 1) no histologic evidence of cervical HSIL and 2) no evidence of HPV-16 or HPV-18 at the Week 36 evaluation. Also, to be considered a responder, the subject must not have had an unscheduled cervical tissue sample obtained between study entry and the Week 36 visit. Conversely, any subject with: 1) histologic evidence of cervical HSIL at the Week 36 evaluation, OR 2) evidence of HPV-16 or HPV-18 at the Week 36 visit, OR 3) a cervical tissue sample obtained between study entry and the Week 36 visit will be designated as a non-responder.

Table 7. Definition of Primary Endpoint Responder and Non-Responder

Responder	Non-Responder
Subject with no histologic evidence of cervical HSIL ^a at Week 36 evaluation and no evidence of HPV-16 or HPV-18 at Week 36	Subject with histologic evidence of cervical HSIL, AIS, cervical carcinoma at Week 36 evaluation OR
AND Subject in which a cervical tissue sample was NOT obtained between collection of tissue to determine entry eligibility up to Week 36 primary endpoint visit	Subject with evidence of HPV-16 or HPV-18 at Week 36 OR Subject in which an additional cervical tissue sample was obtained between collection of tissue to determine entry eligibility up to Week 36 primary endpoint visit

^a no evidence of HSIL is defined by histology as negative, squamous atypia, or LSIL

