6.13 COLPOSCOPY AND CERVICAL BIOPSIES

Colposcopy at screening must be adequate, defined as full visualization of the squamo-columnar junction (Type I or II transformation zone) and complete visualization of the upper limit of aceto-white epithelium or suspected dysplasia. An ECC is not required for study entry. However, if an ECC was done as part of routine care during the screening period, and found to have evidence of cervical HSIL such subject should not be enrolled in the study. Colposcopy is not required to be performed at screening if adequate colposcopy was previously obtained upon collection of initial biopsy. All colposcopies performed after informed consent must be conducted according to the procedures outlined in Appendix C.

Interval colposcopies will be performed at Day 0, Weeks 15, 28, 36, 62, and 88. An unscheduled colposcopy may be performed at the discretion of the investigator if there is suspicion of disease worsening or progression.

Digital photographs of the cervix will be captured during each colposcopic examination to document the clinical findings. If a biopsy or surgical excision is performed, images of the cervix should be collected before and after the procedure. Each site will be instructed on 1) the technique for capturing the proper images using a standard approach and 2) the process for uploading the images to a secure

server. Additionally, after subject is enrolled if vaginal or vulvar lesion should develop, photograph should be taken to document the clinical exam finding.

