6.13.1 ECTOCERVICAL BIOPSIES

Ectocervical biopsies are required at screening to confirm eligibility. If the criteria outlined in Table 5 or 6 are met, ectocervical biopsies may also be performed at Week 36 to provide tissue for histopathologic assessment of disease regression.

Biopsies should not be performed at any other visit unless there is suspicion of disease progression. Removal of additional tissue by biopsy before Week 36 will bias results toward improvement regardless of whether the subject is in the active or placebo group. The bias introduced will obviously be more significant for smaller lesions. For this reason, if biopsies are obtained prior to Week 36, the subject will be treated as a non-regressor. Subject safety is paramount in this study. Therefore, if at any time the investigator may suspect disease progression and the standard of medical care would be to perform an unscheduled biopsy prior to Week 36, then his or her medical judgment should prevail over the default "Schedule of Events", Table 1.

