8.9 EFFICACY ANALYSES

The true treatment effect on the primary endpoint is $\delta = p_V - p_P$, where p_V and p_P denote the true population probabilities of the primary endpoint for VGX-3100X and Placebo, respectively. The primary hypothesis of superiority is:

$$H_0$$
: $\delta \leq 0$ vs. H_1 : $\delta > 0$.

A p-value for this hypothesis test and corresponding 95% confidence interval will be computed based on the method of Miettinen and Nurminen [27]. Superiority will be concluded if the one-sided p-value is <0.025 and the corresponding lower bound of the 95% CI exceeds zero.

The secondary efficacy endpoints will be analyzed in the same manner as the primary hypothesis, but without the hypothesis test p-values.

The histopathologic efficacy time frame is defined by those who have undergone a biopsy or surgical excision at any time starting from 14 days prior to the protocol-specified target date of Week 36. It also includes subjects who underwent early intervention prior to this time frame; these subjects are considered as failures for the efficacy endpoints. Table 13 provides details for the definition of the primary endpoint response.

Table 13. Definition of Primary Endpoint Responder and Non-Responder

Responder	Non-Responder
Subject with no histologic evidence of cervical	Subject with histologic evidence of cervical HSIL, AIS, cervical carcinoma at Week 36 evaluation
HSIL ^a at Week 36 evaluation and no evidence of HPV-16 or HPV-18 at Week 36	OR
AND	Subject with evidence of HPV-16 or HPV-18 at Week 36
Subject in which a cervical tissue sample was NOT obtained between collection of tissue to determine entry eligibility up to Week 36 primary endpoint visit	OR
	Subject in which an additional cervical tissue sample was obtained between collection of tissue to determine entry eligibility up to Week 36 primary endpoint visit

^a no evidence of HSIL is defined by histology as negative, squamous atypia, or LSIL

Exploratory analyses will examine the relationship between the primary efficacy endpoint and a) HLA results, b) colposcopy results, c) cytology results, and d) HPV results. As each of these results are categorical, relationships will be examined with contingency tables and logistic regression models which model the primary endpoint versus these results and treatment group as regressor variables.

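### In the protocol version before 3.0, Section 8.15 fails a woman on suspected progression alone, while the responder tables fail her on this ground only if extra cervical tissue was taken

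*Protocol*

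**What the plan says.** All references are to the protocol version preceding 3.0 unless stated otherwise.

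- **Section 8.15, Missing Values.** "Any subject who had suspected disease progression before Week 36 will be considered a non-regressor regardless of the Week 36 result, even if missing". The sentence before it fixes what the regression outcome means here: "A subject's regression outcome is missing if her CIN grade and HPV clearance at Week 36 cannot be determined".
- **Section 8.9, Table 13 (and the identical Table 7).** The third ground for non-response is that "an additional cervical tissue sample was obtained between collection of tissue to determine entry eligibility" and the Week 36 endpoint visit. The other two grounds are HSIL, AIS or carcinoma on histology, and HPV-16 or HPV-18 positivity. Suspicion is not listed. The text above the table also mentions early intervention before the efficacy time frame and says "these subjects are considered as failures for the efficacy endpoints".
- **Section 2.1.3.** To be a responder, "the subject must not have had an unscheduled cervical tissue sample obtained between study entry and the Week 36 visit".
- **Section 6.13.1.** "if biopsies are obtained prior to Week 36, the subject will be treated as a non-regressor". The reason given is that removing tissue biases the result toward improvement.
- **Section 6.13.** "An unscheduled colposcopy may be performed at the discretion of the investigator if there is suspicion of disease worsening or progression". Section 6.12 likewise lets a Pap result suggesting progression to cancer lead to an ad hoc colposcopy, with biopsy only as a possibility.
- **Version 3.0.** Table 7 keeps the tissue-sample trigger and adds a fourth ground, no Week 36 endpoint result. The summary of changes says missing data will count as failure in the ITT efficacy analysis. The available text of version 3.0 stops within Section 6.1.1, so its Section 8.15 cannot be read.

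**The concern.** These are two classification rules for the primary endpoint, and they can give one woman opposite results. The protocol justifies failing biopsied women by the risk that tissue removal itself removes HSIL and possibly HPV. That reason does not apply when no tissue was taken.

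Section 8.15 would also let an investigator's suspicion, for which the sections compared here give no criterion, override a histology reading made by the blinded Pathology Adjudication Committee together with a valid HPV result. An SAP that adopted either rule would contradict one part of the protocol.

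**Working it through.** **1. Does 8.15 reach the primary endpoint?** Yes. Non-regressor cannot be read as a histology-only term there, because the preceding sentence describes the regression outcome by CIN grade and HPV clearance together, which is the composite primary endpoint.

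**2. Can suspicion occur without tissue?** Yes. Sections 6.12 and 6.13 both permit a colposcopy prompted by suspicion without requiring a biopsy.

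**3. The rules side by side, for a woman suspected before Week 36:**

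| Tissue taken before Week 36 | Week 36 result | Tables 7 and 13 | Section 8.15 |
|---|---|---|---|
| Yes | any | non-responder | failure |
| No | HSIL or HPV-16/18 present | non-responder | failure |
| No | clear on both | **responder** | **failure** |
| No | missing | not classified | failure |

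The third row is the contradiction. In the fourth row the tables are silent. Version 3.0 Table 7 settles that row by counting a missing result as non-response, but it does not settle the third.

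**4. The plan's own power figure.** Inputs from Section 8.3: 165 randomized 2:1, 90% evaluable, 40% versus 15%, power 90%. From Section 8.9: one-sided 0.025, Miettinen-Nurminen. Evaluable total: 165 × 0.9 = 148.5, or about 99 and 50. The normal-approximation formula gives 90.2%. Exact enumeration of the score test with 99 and 50 gives 90.4%. The stated 90% reproduces.

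**5. Illustration of size.** Let f be the share of table-defined responders who were suspected but not biopsied. No value of f is given, so the values below are assumptions, taken equal in both arms. Under 8.15 each rate is multiplied by (1 − f). Exact power:

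| f (assumed) | 99 vs 50, 40% vs 15% | 132 vs 66, 35% vs 14% (version 3.0 design) |
|---|---|---|
| 0 | 90.4% | 90.8% |
| 3% | 89.0% | 89.6% |
| 5% | 88.1% | 88.7% |
| 10% | 85.4% | 86.2% |

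At f = 3% the expected number of recoded women is 0.03 × 0.40 × 99 = 1.2 active and 0.03 × 0.15 × 50 = 0.2 placebo. In the version 3.0 design it is 0.03 × 0.35 × 132 = 1.4 and 0.03 × 0.14 × 66 = 0.3.

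**6. Can one woman matter?** Only in a borderline result. With 8/50 responders on placebo, 31/99 on active gives one-sided p = 0.0227 and 30/99 gives p = 0.0297, on either side of 0.025.

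**The case against.** **Superseded text.** The sentence belongs to the version before 3.0. The summary of changes says Section 8 was modified for missing data, and it lists only significant changes, so its silence on this sentence proves nothing. This stands. A reader might infer that version 3.0 carries the same contradiction, but the documents do not support that: its visible rules all use the tissue trigger, and its Section 8.15 cannot be seen.

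**Loose shorthand.** Section 6.13.1 and Appendix C link interval biopsy to suspected progression, and 6.13.1 uses the same term, non-regressor. Section 8.15 may simply have meant the biopsy rule. That is plausible as intent, but the sentence does not mention tissue, and Sections 6.12 and 6.13 separate suspicion from biopsy. As written, the rules differ.

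**Size.** A reader might take the 11 unscheduled biopsies in Phase 2b, against 167 women enrolled (11/167 = 6.6%), as the share affected. It is not. Biopsied women fail under both rules, the figure counts biopsies over the whole study, and the number suspected but not biopsied is not reported.

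**Harm.** A reader might also infer inflated type I error, or freedom to choose a rule after seeing the data. Neither is shown. Investigators are blinded, the recoding would apply in both arms, and an SAP that is not shown may fix the derivation. Section 8.15 does say that suspicion outranks the Week 36 result. It does not say whether 8.15 or Table 13 governs.

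**Conclusion.** The contradiction holds for the version before 3.0 and concerns who counts as a responder on the primary endpoint. It is confined to women suspected of progression, not biopsied, and clear on both histology and HPV at Week 36. Their number is unknown and probably small. If an assumed 3% of responders in each arm were recoded, power would fall by 1.2 to 1.4 points; at an assumed 10%, by 4.6 to 5.0 points. These figures rest entirely on the assumed share and on its being equal in the two arms.

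The sample size calculation is not wrong, and nothing here shows bias in favour of the active arm. The point is worth correcting because an unadjudicated impression should not displace an adjudicated result through a sentence that conflicts with the endpoint tables. Whether it remains open in version 3.0 has to be checked in that version's Section 8.15.

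**What to change.** Reconcile Section 8.15 with the endpoint definition in Tables 7 and 13. It should state that a woman is a non-responder if an additional cervical tissue sample was obtained between the eligibility biopsy and the Week 36 endpoint procedure, and that suspicion of progression without a tissue sample does not override a valid Week 36 result.

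In version 3.0, check whether the suspected-progression sentence is still in Section 8.15. If it is, replace it in the same way and leave missing Week 36 results to the missing-as-failure rule already in that version's Table 7. Carry the same wording into the SAP before unblinding.

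The cost is one sentence. It needs no additional data and does not touch the investigator's discretion over colposcopy or biopsy.
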